Question 1A: What are the most acceptable and easily understood ways to present materials and messages to HCWs, as well as, their family members and networks?

Question 1B: Are the same messages appropriate for Black and Latinx minority communities?

Question 1C: How can available intervention materials be best adapted to optimize acceptability to Black and Latinx minority communities?

Aim 2: Conduct a mixed methods study to evaluate the effectiveness and cost of a HCW focused outreach intervention strategy versus standard community engaged outreach to explore contextual factors (individual, family, and community) affecting COVID-19 testing implementation outcomes and scalability. In Phase 2, lower-income index HCWs (from our cohorts, as well as, the Visiting Nurse Association, and Parker Health) serve as ambassadors to offer testing to their “spheres of influence” (households/contacts).

Hypothesis 2A: A participatory outreach strategy approach focused on identified index HCWs will mobilize quicker uptake of testing within community settings than best practice, community recruitment approaches.

Hypothesis 2B: Recruitment through index HCWs will be more successful for hard to reach participants compared to a traditional community based organization approach.

Question 2A: What are the costs of implementing NJ HEROES TOO for healthcare and community organizations?

Question 2B: What lessons have we learned about implementation and opportunities for sustainment?

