The RWJSS involves 3904 hospital employees and affiliated clinicians who received SARS-CoV-2 virus and antibody testing at a single time-point and are being followed for self-reported COVID-19 prospectively. 1202 (30.8%) tested participants are URM. A total of 9.8% of participants tested positive for SARS-CoV-2 virus or antibodies, with higher rates observed among Black (14.8%) and Latinx (15.5%) HCW. Notably, compared to non-Hispanic White participants, the odds of a positive test were twofold higher among Black (OR: 2.15, 95% CI: 1.55, 2.97) and Latinx participants (OR: 1.94, 95% CI: 1.42, 2.66). Importantly, infection rates were especially high among lower status medical roles (e.g., technicians, phlebotomists) as well as hospital support roles (dining/food, maintenance /housekeeping, security/support) (Figure 7).

Figure 7. Prevalence of SARS-CoV-2 infection based on role in the hospital and direct patient care responsibilities

Notes: ED, emergency department; EMT, emergency medical technician; NP, nurse practitioner; OR, operating room; PA, physician's assistant; PT, physical therapist; OT, occupational therapist; RT, respiratory therapist; ST, speech therapist

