1.5 Sample Size Justification

For Phase 1, Virtual Community Conversations we will convene 8-10 community focus group conversations of 10-12 ethnically homogenous participants each representing Black and Latinx stakeholders (i.e., healthcare workers, family members and community organizers). The literature suggests that for our purposes, 2-3 focus groups are sufficient to capture 80% of themes, including the most prevalent themes, and three to six groups for 90% of themes in a homogeneous study population using a semistructured discussion guide.³⁷ To reach the desired number of 15-20 healthcare workers we will supplement community conversations with individual key informant interviews with healthcare workers given they have not been able to participate in group meetings. Hennick et al suggest code saturation can be established with as few as 6 interviews with full saturation reached at nine interviews.³⁸ They determined the first interview conducted contributes more than half (53%) of new codes and three quarters (75%) of high-prevalence codes, with subsequent interviews adding a few new codes each until saturation.³⁸

Rate (expected #/month) in NJ HEROES TOO arm			
RR	80	100	120
1.15	0.78	0.82	0.81
1.2	0.94	0.96	0.95
1.3	0.99	0.99	0.99

For Phase 2, to test our Aim 2A hypothesis which compares testing uptake between the two arms power calculations are based on the primary outcome measure, testing uptake rate. We report power for rate ratios (RR; ratio of rate in comparison arm relative to intervention arm) of 1.15, 1.2, and 1.3, when expected tests per month in the intervention arm range from 80 to 120 (Table). We will have about 80% power or greater for RR of 1.15 or greater. To test hypothesis 2B, we will compare participants in the two arms on key

characteristics that may be barriers to testing (participant trust, health literacy, English proficiency and patient activation). We will do so through linear regression models, adjusting for covariates including participant age, race/ethnicity, sex, and highest level of educational attainment.

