Electronic survey data collection: Interested individuals can click active hyperlinks, scan QR codes or type in URLs from recruitment materials to obtain more information on the study and assess their eligibility. Informed consent will be collected electronically after which consented individuals will complete demographic questionnaires about themselves and their households. They will then be asked to extend the invitation to their "spheres of influence" (household and other family members/community contacts) to reach populations who would not otherwise have access to testing. The ambassadors will receive an e-mail and/or text message with an URL link to forward to their contacts. By clicking that link, the household and other family member/community contact will be taken to a webpage with information on NJ HEROES TOO testing, including contact information for study staff.

Telephone data collection: For individuals who are not able to enter their own information electronically, a phone number will be provided for the study. They can use it to reach a research staff member who will consent them, administer the survey by phone and set them up with Vault Health for testing.

Recruitment of the community-based comparison group arm (Aim 2). For the traditional, community based arm of study aim 2, recruitment will be channeled through extant community-based organizations focused on underserved communities in the counties of interest. These partner organizations will advertise the testing opportunity through their preferred standard community outreach channels (e.g. mailings, flyers, community events) as well as through additional multimedia approaches identified and developed during Aim 1. As in the NJ HEROES TOO arm, interested individuals can either opt for electronic or telephone data collection.

C. Subject Screening

▪ Eligibility Criteria

Aim 1: (1) self-identification as Black or Latinx; (2) age 18 or older; and, (3) have access to phone, internet and/or email/text messages; and, (4) ability to speak, understand, and/or read English or Spanish.

Aim 2 Healthcare Workers: (1) self-identification as Black or Latinx; (2) employment at one of the participating health care settings (Parker Health, Robert Wood Johnson University Hospital, University Hospital, Visiting Nurse Association); (3) resident of Union, Passaic, Middlesex, or Essex County, NJ; and, (4) age 18 or older..

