Quantitative: To compare participation rates in the two arms, our primary outcome, we will use data on the number of tests performed per month (over the up to 12 month study period). For each intervention, the start time is the date of first attempted contact with potential participants and the end date is either the end of the study period, or the date at which the 1000th individual was tested (whichever comes first). We assume that the number tested follows a Poisson distribution within the time period. We will test the null hypothesis that there is no difference between the two interventions, and also report a 95% confidence interval for the rate ratio. Secondly, we will examine the proportion of tested participants from vulnerable and underserved populations of interest (e.g. Black and Latinx, immigrants, children, and low-income households) in each arm through logistic regression models. We will additionally examine proportion of positive tests in the two study arms to examine whether recruitment through index HCWs taps into more highly exposed participant groups, as hypothesized. To do so we will fit logistic regression models, where the outcome is positive test results (yes/no) and the primary predictor is study arm, adjusting for covariates including participant age, race/ethnicity, sex, occupation, and highest level of educational attainment. Power calculations for this aim are based on the primary outcome measure, testing uptake rate. We report power for rate ratios (RR; ratio of rate in comparison arm relative to intervention arm) of 1.15, 1.2, and 1.3, when expected tests per month in the intervention arm range from 80 to 120 (Table X). We will have about 80% power or greater for RR of 1.15 or greater. To test hypothesis 2B, we will compare participants in the two arms on key characteristics that may be barriers to testing (participant trust, health literacy, English proficiency, and patient activation). We will do so through linear regression models, adjusting for covariates including participant age, race/ethnicity, sex, and highest level of educational attainment.

RR	80	100	120
1.15	0.78	0.82	0.81
1.2	0.94	0.96	0.95
1.3	0.99	0.99	0.99

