Cost Analysis: The cost of the intervention components will be calculated using wage rates for personnel at the healthcare organizations and CBOs involved in distribution of materials multiplied by time recorded in time logs. Fringe benefit costs (healthcare, disability, and life insurance) will be added to wages by applying the prevailing fringe benefit rate. The value of time will be calculated as the present value of earnings: (number of hours spent delivering NJ HEROES TOO components) x (interventionist's reported wage rates + fringe benefits). Staff training time will be captured and converted to costs based on application of hourly wage rates. Material costs will include the salivary test, educational print materials provided to study participants, and any other required supplies.

Qualitative/Process Analysis: We will conduct an ongoing mixed methods process evaluation to gather data on how the interventions are implemented while gaining critical insight into factors that influence implementation from multiple perspectives. We will collect quantitative and qualitative data on key intervention components to understand reach, engagement, and adoption of the interventions. Data on reach will assess number of family members/contacts per HCW enrolled. Data on engagement will include data on participation rates for HCWs and families participating across the four counties. Data on adoption will include distribution of educational materials and testing uptake across the four counties. Throughout the intervention, we will purposefully identify and select key informants, individuals with direct experience and knowledge about the intervention, including both those implementing the intervention and recipients of the intervention.

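### The models for test positivity and the four hypothesis 2B barrier measures hold education (and, for positivity, occupation) fixed, so they leave out part of the question of who each route reaches

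*Combined protocol and SAP*

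**What the plan says.** Section 6.1 (Data Analysis, Aim 2, Quantitative) states the purpose of the positivity comparison: "to examine whether recruitment through index HCWs taps into more highly exposed participant groups, as hypothesized". The next sentence gives the method, a logistic model with study arm as main predictor, "adjusting for covariates including participant age, race/ethnicity, sex, occupation, and highest level of educational attainment".

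Hypothesis 2B in Section 1.1 reads: "Recruitment through index HCWs will be more successful for hard to reach participants compared to a traditional community based organization approach". Sections 1.5 and 6.1 test it by comparing the arms on four barrier measures (patient activation, English proficiency, health literacy and trust). Both sections give the same method for this: "We will do so through linear regression models, adjusting for covariates including participant age, race/ethnicity, sex, and highest level of educational attainment".

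Neither section specifies a contrast without these covariates for any of the five outcomes. Two other arm comparisons in Section 6.1 name no covariates: the primary rate ratio, and the share of tested participants from vulnerable groups (for example immigrants, children and low-income households).

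Three other places bear on the point:
- Section 4.1 makes employment at a participating healthcare setting an entry condition for index HCWs.
- Section 1.4 reports that in the team's hospital cohort "infection rates were especially high among lower status medical roles (e.g., technicians, phlebotomists) as well as hospital support roles".
- The process evaluation in Section 6.1 measures reach through contacts: "Data on reach will assess number of family members/contacts per HCW enrolled".

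**The concern.** Both questions concern the composition of the group that each route brings in. A coefficient at equal education and occupation answers a different one: do the arms differ among people with the same schooling and the same kind of job? If the HCW route finds more infection because it reaches people in riskier jobs, the occupation term absorbs that. If one route reaches people with less schooling and therefore lower health literacy, the education term absorbs that.

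At stake is how a null result is read. An adjusted coefficient near zero could be reported as showing that the HCW route does not reach more exposed or harder-to-reach people, when a difference exists but runs through job or education. Adjustment could also enlarge or reverse the arm difference.

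**Working it through.** The plan gives no figure for these models; its power table concerns the uptake rate only. There is nothing to reproduce. The inputs below are assumed, except the approximately 1000 per arm, which is the enrolment goal in Section 4.3. The 500 tested per arm is an assumed lower case, since that section reports low testing uptake.

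**Positivity.** Assume 15% positive in healthcare jobs and 8% otherwise, and a healthcare-job share of 30% or 50% in the HCW arm against 5% in the CBO arm. Arm risk = share × 0.15 + (1 − share) × 0.08.
- HCW arm: 0.30 × 0.15 + 0.70 × 0.08 = 0.1010, or 0.50 × 0.15 + 0.50 × 0.08 = 0.1150.
- CBO arm: 0.05 × 0.15 + 0.95 × 0.08 = 0.0835.
- Crude odds ratio (OR): 1.23 or 1.43. The OR at equal occupation is 1.00 by construction, since the arms were assumed to differ only through occupation.

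Precision, with SE of the log OR = √(sum of the reciprocals of the four expected cell counts), two-sided 0.05, independent participants:

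| Positivity (healthcare job / other) | Tested per arm | Crude OR | Power |
|---|---|---|---|
| 15% / 8% | 1000 | 1.23 to 1.43 | 0.27 to 0.65 |
| 15% / 8% | 500 | 1.23 to 1.43 | 0.16 to 0.38 |
| 3% / 1.6% | 1000 | 1.21 to 1.39 | 0.09 to 0.17 |
| 3% / 1.6% | 500 | 1.21 to 1.39 | 0.07 to 0.11 |

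In the first row the SEs are 0.155 and 0.151, and the 95% CIs are 0.91 to 1.67 and 1.06 to 1.92.

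**Why the pooled crude contrast is not enough.** Suppose all index HCWs hold healthcare jobs, and HCW-arm contacts have the CBO arm's 5% share. The index fraction is then (share − 0.05)/0.95 = 0.263 or 0.474.
- Pooled risk: 0.263 × 0.15 + 0.737 × 0.0835 = 0.1010, or 0.474 × 0.15 + 0.526 × 0.0835 = 0.1150. These equal the risks above, so the pooled OR is again 1.23 or 1.43.
- Index HCWs against CBO: 0.15 against 0.0835, OR 1.94.
- Contacts against CBO: 0.0835 against 0.0835, OR 1.00. With 737 or 526 contacts per arm (same split assumed in the CBO arm), the CI is 0.69 to 1.45 or 0.65 to 1.55.

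Here the whole pooled excess is the entry criterion, and none of it is reach to contacts.

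**Clustering.** Recruitment runs through households and networks. With an assumed cluster size of 3 and intraclass correlation of 0.3, the design effect is 1 + (3 − 1) × 0.3 = 1.6. The best-case power of 0.65 falls to about 0.46, and the contact interval of 0.69 to 1.45 widens to about 0.63 to 1.6.

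**2B measures.** In a linear model with education as the only covariate that differs between arms, unadjusted minus adjusted arm coefficient = education effect × arm difference in low-education share. Assume an education effect of 0.4 to 0.8 SD and a share difference of 10 to 20 points. The omitted part is then 0.4 × 0.10 = 0.04 SD to 0.8 × 0.20 = 0.16 SD. The 95% CI half-width at 1000 per arm is 1.96 × √(2/1000) = 0.088 SD with independent participants. If education is balanced across arms, the omitted part is zero.

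**The case against.** Several points on the other side have force.

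- **Adjusting for occupation can be defended.** The HCW arm contains healthcare workers by design. In the split example the adjusted OR of 1.00 is the right answer for contacts, and the pooled crude OR is the misleading one. A reader might infer that the pooled crude contrast is simply the correct estimate of reach. The documents do not support that: Sections 4.1 and 6.1 place reach in household members and contacts. This stands, and it is why the split is needed.
- **The arms are recruited by different routes, with no randomization described, so adjustment is natural.** That holds for a causal effect of route on infection. Here the stated question is who was recruited. The adjusted models should stay, labelled for what they estimate.
- **The plan may intend raw proportions anyway.** It speaks of examining the proportion of positive tests by arm, and its covariate lists are open-ended. That does not exclude a crude contrast, but the sentence giving the method names only the adjusted model.
- **Vulnerable-group proportions already address composition.** In part they do, so a null 2B coefficient would not be the only evidence. They are still different outcomes.
- **Age, sex and race/ethnicity also describe composition.** Correct. Children are a named population of interest, so holding age fixed would remove reach through children. The reach contrast should therefore be fully unadjusted. Occupation is also hard to define for participants aged 4 to 17.
- **The sizes are invented.** They illustrate a mechanism only. The hospital cohort compares roles among staff on virus or antibody, so it gives no size for saliva positivity against a community group.

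**Conclusion.** The concern holds for five secondary outcomes: positivity and the four 2B measures. As specified, their arm coefficients leave out any difference in reach that runs through education and, for positivity, occupation. That follows from the text alone. Every figure above rests on assumed shares, risks and education effects; size and direction cannot be known from the documents.

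Three stronger readings are not supported. A reader might infer that the adjusted models are wrong and should be dropped; they answer a legitimate conditional question. A reader might infer that the plan will hide a true effect; if education and occupation are balanced, little or nothing is omitted. A reader might infer that low testing uptake also shrinks the 2B sample; the survey precedes testing (Section 1.3), Section 4.3 says survey completion is high, and 2B is not stated to be limited to tested participants.

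The change is worth making because it costs little and alters what a null may be taken to mean. It will not yield a well-powered test of positivity: power is 0.07 to 0.65 under the assumed inputs, and lower with clustering.

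**What to change.** In Section 6.1, and for 2B also in Section 1.5:

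1. For each 2B measure, specify the unadjusted arm difference in means with a 95% CI as the estimate for the reach question. Keep the planned model beside it, labelled as the difference at equal age, race/ethnicity, sex and education.
2. For positivity, report the unadjusted proportions and their arm contrast with a 95% CI beside the adjusted model. Show them for all participants, and separately for index participants and for household members/contacts. State that the pooled contrast alone is not to be read as reach, because it includes the HCW entry criterion.
3. If contact status is not recorded in the CBO arm, compare HCW-arm contacts with all CBO participants and state that this mixes recruitment levels. Section 4.1 lists household members/contacts separately in both arms but does not say how this is stored.
4. Use standard errors that allow for clustering within households or ambassador networks wherever linkage is recorded.
5. Describe all of these as descriptive secondary estimates.

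The cost is a few sentences and a few more estimates to report, with no change to enrolment. The planned count of contacts per HCW already needs contact status in that arm. The downside is that an unadjusted contrast does not separate the pathways behind a difference.

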Recruitment of NJ HEROES TOO arm (Aim 2). In this arm of study aim 2, we will recruit low income health care workers (HCW) employed at several NJ healthcare centers in affected counties to be “ambassadors” to help extend recruitment to their family members and community contacts. We will do so through our two current HCW cohorts, the Rutgers Corona Cohort (RCC) and the Robert Wood Johnson Screening Study (RWJSS) (total Black and Latinx n~1300) which have recruited participants at University Hospital and Robert Wood Johnson University Hospital. Additionally, to increase the reach of our HCW intervention beyond academic medical and healthcare system settings, we have partnered with Parker Health (representing nursing home and assisted living facility HCWs) based in Middlesex county and the Visiting Nurse Association Health Group (VNA), which is a statewide home healthcare organization with significant activities in Essex, Union and Passaic counties. Specifically, the organizations will: (1) inform prospective subjects about the availability of the research (e.g.,

announce the study at meetings with their staff, post links to the study website on their website, on their list serves, in their newsletters and social media); (2) provide prospective subjects with information about the research (i.e., share recruitment materials with their staff); (3) provide prospective subjects from their staff with information about contacting investigators for information or enrollment; and/or (4) ask their staff permission for investigators to contact them.

These approaches leverage trusted relationships (with the HCW), use culturally and linguistically responsive materials, and reduce the burden of testing by using mailed saliva kits to address common barriers encountered by the targeted populations. Campaign materials will also include lists of community resources that can provide support in the event of positive test result, since the potential effects of a positive result and quarantine on employment and a person's ability to meet basic needs are themselves significant barriers. Where applicable (such as in our ongoing cohorts), we will send e-mail blasts/flyers, and place posters and informational kiosks in key hospital and clinical locations. Recruitment materials in English have been developed are part of this protocol amendment. Once they have been approved we will submit Spanish translations for IRB for approval prior to their use.

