4.3 Number of Subjects

A. Total Number of Subjects

We anticipate a total of 3000 participants will be enrolled across the two study aims.

Aim 1: We recruited 13 groups and 8 individual interviews with stakeholders who identified as Black and/or Latinx (n=111 individuals).

Aim 2: The goal is to enroll approximately 1000 participants in each of the two study arms (N=2000) over a 12 month period.

We are experiencing a high loss to follow-up rate in Aim 2. Though interest, consent rates and survey completion are high there is also a high rate of loss to follow-up. COVID-19 testing is the study outcome and uptake among participants is low. Therefore, we may need to enroll more than 1000 per arm.

B. Total Number of Subjects If Multicenter Study

N/A

C. Feasibility

For Aim 1 and Aim 2 community based organization arm, drawing from long-established relationships and community partners of MPIs [name], [name], and [name] we have engaged 18 community organizations in the design and development of this project. Organizations serve the cities of Newark, Elizabeth, Irvington, Hillside, Caldwell, Paterson, New Brunswick, Perth Amboy, and their surrounding areas. They range in size, scope and focus from faith-based organizations to large social service groups.

For the Aim 2 HCW arm, our current COVID-19 surveillance cohorts include nearly 4000 HCWs, of whom we estimate 32% (n~1300) meet criteria to serve as ambassadors. We anticipate that approximately 1000 more HCWs from Parker Health and the Visiting Nurse Association will be eligible.

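### County of residence is not among the named covariates of the positivity and Hypothesis 2B models, although the arms recruit through different partner organisations; an imbalance is possible but not shown

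*Combined protocol and SAP*

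**What the plan says.** **How the arms are formed (sections 4.1 and 4.3).** The healthcare worker (HCW) arm starts from two cohorts "which have recruited participants at University Hospital and Robert Wood Johnson University Hospital", from "Parker Health (representing nursing home and assisted living facility HCWs) based in Middlesex county", and from the Visiting Nurse Association, a "statewide home healthcare organization with significant activities in Essex, Union and Passaic counties". Ambassadors then invite household members and contacts. The comparison arm is recruited by 18 community organisations, described in 4.3: "Organizations serve the cities of Newark, Elizabeth, Irvington, Hillside, Caldwell, Paterson, New Brunswick, Perth Amboy, and their surrounding areas". Every Aim 2 adult group must live in Union, Passaic, Middlesex or Essex County. No randomisation, matching or county quota is described.

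**How the arms are compared (section 6.1; 1.5 repeats the 2B part).** The positivity logistic model is fitted "adjusting for covariates including participant age, race/ethnicity, sex, occupation, and highest level of educational attainment". The Hypothesis 2B linear models (trust, health literacy, English proficiency, patient activation) list age, race/ethnicity, sex and education. Neither list names county or any other place variable. County appears only in the descriptive process evaluation, where adoption data cover "testing uptake across the four counties".

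**How the result is to be read.** Section 6.1 uses the positivity contrast to judge whether recruitment through index HCWs reaches more highly exposed people.

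**The concern.** With channel-defined arms, only the model can separate the recruitment route from the places where each channel's partners operate. The plan adjusts for who the participants are but does not name where they live. Section 1.2 itself says that COVID-19 cases, poverty and minority residence overlap by area within the state.

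Suppose one arm's participants come more from a county with more infection. The arm odds ratio would then move away from 1 even if, within each county, both channels recruited people at equal risk. It could move either way, depending on which arm is over-represented there. The same holds for 2B measures that may vary by area, such as English proficiency and health literacy. At stake is the attribution of two secondary findings to the HCW route, not the primary result.

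**Working it through.** The plan states no effect size or power for these models, so there is no figure of its own to reproduce. It also gives no county positivity and no county mix by arm. What follows is an illustration on assumed values.

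**Inputs from the documents.** About 1000 per arm is the enrolment goal (4.3), but 4.3 also reports low testing uptake, so 300 tested per arm is shown too (assumed). The 9.8% positive for virus or antibody in the hospital employee cohort (1.4) serves only as a high reference level.

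**Assumptions.** There are two groups of places, with no arm effect within a place. The test is two-sided at 0.05 and no other covariate carries the place difference.

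**Formulas.** With lower-place positivity L, ratio r, and shares a and b of each arm from the higher place:
- p1 = a·rL + (1 − a)·L and p2 = b·rL + (1 − b)·L
- OR = [p1/(1 − p1)] / [p2/(1 − p2)]
- SE = √{[p1(1 − p1) + p2(1 − p2)]/n} and z = (p1 − p2)/SE
- P(reject) = Φ(z − 1.96) + Φ(−z − 1.96)

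**Worked case.** Mean positivity 5% and r = 2 give L = 2 × 0.05/(1 + 2) = 0.0333. With a = 0.7 and b = 0.3:
- p1 = 0.7 × 0.0667 + 0.3 × 0.0333 = 0.0567
- p2 = 0.3 × 0.0667 + 0.7 × 0.0333 = 0.0433
- OR = 1.33
- At n = 1000, SE = 0.00974, z = 1.37 and P(reject) = 28%.

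| L | r | Shares a / b | p1 vs p2 | Spurious OR | P(reject), 1000 per arm | P(reject), 300 per arm |
|---|---|---|---|---|---|---|
| 3% | 1.25 | 60 / 40 | 3.45% vs 3.30% | 1.05 | 5% | 5% |
| 5% | 1.5 | 70 / 30 | 6.75% vs 5.75% | 1.19 | 15% | 8% |
| 3.33% | 2 | 70 / 30 | 5.67% vs 4.33% | 1.33 | 28% | 12% |
| 9.8% | 2 | 80 / 30 | 17.64% vs 12.74% | 1.47 | 86% | 39% |
| 2.5% | 3 | 70 / 30 | 6.00% vs 4.00% | 1.53 | 54% | 20% |

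Swapping the arms inverts each OR. Fewer tests lower the rejection rate but leave the bias unchanged.

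**Barrier scores.** Bias = (place difference in SD) × (a − b), with SE = √(2/1000) = 0.0447 SD.
- A difference of 0.1 SD at 60 / 40 gives 0.02 SD and about 7% rejections.
- A difference of 0.2 SD at 70 / 30 gives 0.08 SD and about 43%.

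**Effect of adding county.** This is a four-county logistic simulation with no arm effect, 1000 per arm, assumed county positivity of 4% to 8%, and 400 runs. The Monte Carlo SE at 5% is √(0.05 × 0.95/400) = 1.1 points.

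| Assumed county mix | Without county: OR, rejections | With county: OR, rejections | SE of log OR |
|---|---|---|---|
| Same in both arms | 1.00, 5.0% | 1.00, 4.5% | 0.189 → 0.190 |
| Moderately different | 0.86, 14% | 0.99, 6.3% | 0.193 → 0.200 |
| Strongly different | 0.75, 31% | 0.99, 6.3% | 0.195 → 0.229 |
| Strongly different, reversed pattern | 1.35, 34% | 0.99, 5.5% | 0.196 → 0.227 |

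The SE rises by 0.200/0.193 − 1 = 4% in the moderate case, and by 0.229/0.195 − 1 = 17% or 0.227/0.196 − 1 = 16% in the strong cases.

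**The case against.** **No imbalance is shown.** Both arms require residence in the same four counties. The HCW partners named in 4.1 reach all four, and Newark is both the site of University Hospital and first on the community organisations' city list. With equal county mixes the bias is nil. This stands, and it limits the claim to a possibility.

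**Employer shares do not fill the gap.** A reader might take the cohort figure, "1202 (30.8%) tested participants are URM", divide by the roughly 2300 expected eligible HCWs in 4.3 (1300 + 1000), get 52%, and infer that the HCW arm is concentrated in one locality. The documents do not support that. The 1202 are counted before the residence criterion is applied, their counties are not given, and ambassadors only seed an arm that also contains their contacts. Nor does the statewide overlap in section 1.2 establish that positivity differs among these four counties.

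**The lists are open.** Both use the word including, so county is unspecified rather than excluded. That is correct. It also means that county could be added or left out after the results are known.

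**County adjustment may remove part of the answer.** Both questions ask who is reached. If HCW networks reach residents of higher-infection areas or areas with lower English proficiency, that may be part of what the strategy achieves. This stands against relying on the adjusted coefficient alone, so both estimates are needed.

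**The cost is not always small.** The SE rises most where adjustment matters most. With 300 tested per arm and 2% to 5% positive there would be only 600 × 0.02 = 12 to 600 × 0.05 = 30 positive tests, for a model that already holds arm and five covariates. This stands, and the fix allows for it.

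**Conclusion.** The point holds as a gap in pre-specification. Arms are formed by channel without any device to balance county, and neither the positivity model nor the 2B models name it. A difference due to where partners operate therefore cannot be told apart from one due to the recruitment route.

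The size is unknown. Across the assumed rates and mixes the spurious odds ratio runs from near 1 to about 1.5, or the inverse, and the chance of false significance runs from about the nominal 5% to well above it. All of this rests on assumed county rates and mixes.

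The documents do not support the stronger conclusions that the arms are geographically imbalanced, that the planned estimates are biased, or that any bias favours the HCW arm. The change is worth making before the analysis, for these secondary models only.

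**What to change.** In section 6.1, and in 1.5 for the 2B models:

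1. Tabulate arm by county of residence among those tested and those surveyed.
2. Fit the positivity logistic model and the four 2B linear models a second time with county added (four levels, 3 degrees of freedom). Report the county-adjusted arm coefficient beside the planned one.
3. State that a difference will be attributed to the HCW recruitment route, rather than to partner location, only if it persists after county adjustment. Otherwise it will be described as a difference in the populations and places reached.
4. State in advance what will be done if positive tests are few, for example collapsing counties or using a penalised fit.
5. Name county as an analysis variable, so that it is kept when identifiers are removed at export (sections 1.9 and 6.3).

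**Cost.** No new data should be needed, since residence is an eligibility item and an address is entered for the kit (4.4). Precision falls by the amounts shown above, and information is lost if a county has participants from only one arm. County is coarse, so differences within a county remain. The primary Poisson rate ratio needs no change for this point.
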